6.1.19 Follow-up Period

Safety Follow-up

All patients who have completed an EOT Visit will have a Safety Follow-up Visit. The Safety Follow-up Visit will be conducted at 30 days (± 7 days) from EOT Visit.

AEs related to the study drug will be followed until resolution and SAEs will be followed until resolution regardless of the relationship to the study drug.

All female patients of childbearing potential must complete a pregnancy test (serum or urine) during the Safety Follow-up Visit. Pregnancy testing should be repeated for patients with suspected pregnancy. This is not applicable for postmenopausal female patients (defined as at least 12 months of amenorrhea without alternative medical cause), and the date of menopause should be recorded instead.

Efficacy Follow-up

Patients who discontinue the study drug due to reasons other than disease progression, death, lost to follow-up, or withdrawal of consent will remain on study for tumor assessments and will be followed every 12 weeks (± 14 days) from the EOT visit or last assessment, until disease progression, initiation of new anticancer therapy, withdrawal of consent, lost to follow-up, death, conditions are met per Section [6.2.1](#), or the end of the study, whichever comes first.

Survival Follow-up

All patients will be followed for survival status every 12 weeks (± 14 days), until death, lost to follow-up, or withdrawal of consent. Survival information can be obtained via phone and information will be documented in the source documents and relevant CRFs.

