3.1.5. Response Evaluable Analysis Set

The response evaluable analysis set will include all patients who are in the efficacy analysis set and have a baseline tumor assessment, and either (i) have at least 1 post-dose evaluable tumor assessment, or (ii) do not have post-dose tumor assessment, but have clinical progression as noted by the investigator or have died due to any cause before their second post-dose tumor assessment. The response evaluable analysis set will be used for analyses of anti-tumor response.

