4.2. Efficacy Endpoints

4.2.1. Best Overall Response

Assessment of anti-tumor response for patients with AML will be conducted according to 2017 European Leukemia Net (ELN) criteria (Döhner et al, 2017). Best overall response (BOR) is defined as the best response during the anti-tumor evaluation period, which will be determined using time point responses (TPRs) from date of the first dose of study treatment from Cycle 1 in continuous cycle (i.e. not from the date of single oral dose from the PK week for the dose escalation part) up until the last evaluable TPR prior to or on the date of (i) disease progression (at least 2 cycles of study drug should be administered to determine PD) / relapse according to the 2017 ELN criteria, or death; or (ii) withdrawal of consent or lost to follow-up; or (iii) receiving subsequent anti-cancer therapy, whichever is earlier.

The hierarchical order of these response categories is complete response with negative minimal residual disease (CR_{MRD-}) > complete response (CR) > complete response with partial hematological recovery (CRh) > complete response with incomplete count (CRI) > morphologically leukemia-free state (MLFS) > partial response (PR) > stable disease (SD) > progressive disease (PD) > NE (not evaluable), where CR_{MRD-} , CR and CRI are based on investigator assessment of response, and CRh will be derived from relevant data including investigator-collected bone marrow and hematology data by medical team as external file, as CRh is not defined in ELN 2017. This order will be used to derive the BOR. For example, a patient who has 4 anti-tumor assessments during the anti-tumor evaluation period with response being MLFS, PR, SD, and PD respectively, then the BOR for this patient will be MLFS.

Of note, for the BOR being SD, it is expected that the duration of SD lasts for at least 3 cycles, for example, if a patient only has one tumor assessment at 2 cycles with response being SD, then, the BOR for this patient will be NE instead. For the BOR being PD, at least 2 cycles of study drug should be administered, for example, if a patient only has one tumor assessment at 1 cycle of study drug with response being PD, then, the BOR for this patient will be NE instead.

Moreover, subjects who do not have post-dose tumor assessment, but have clinical progression as noted by the investigator or have died due to any cause before their second post-dose tumor assessment, BOR will be PD.

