For patients whose BOR is 'NE', reasons for NE will be summarized as followings:

- All post-baseline overall responses are NE / No baseline or post-baseline assessments;
- Initiation of subsequent anti-tumor therapy prior to the first post-baseline tumor assessment;
- SD lasts less than 3 cycles;
- Less than 2 cycles of study drug to determine PD.

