4.2.7. Progression-free Survival

Progression-free Survival (PFS) is defined as the time (months) from the start of study treatment from Cycle 1 in continuous cycle (i.e. not from the date of single oral dose from the PK week for the dose escalation part) to disease progression, or relapse, or death due to any cause, whichever occurs first. More specifically, PFS will be determined using all the assessment data up until the last evaluable visit prior to or on the date of

- (i) disease progression (at least 2 cycles of study drug should be administered to determine PD) or relapse as defined by 2017 ELN criteria for AML patients, or
- (ii) withdrawal of consent; or lost to follow-up, or
- (iii) receiving subsequent anti-tumor therapy, whichever is earlier.

Patients without report of PD or death due to any cause at the time of analysis are censored as described in [Table 7](#) below.

Table 7 Outcome and Event or Censoring Dates for PFS

Rule	Situation	Date of Progression or Censoring	Outcome
------	-----------	----------------------------------	---------

1	PD/relapse documented between schedule tumor assessment visit or after one missing tumor assessment visit	Date of first documented disease progression/relapse	Event
2	Death without PD/relapse between schedule tumor assessment visit or death on or before the second scheduled visit or death after one missing tumor assessment visit	Date of death	Event
3	No baseline or post-baseline tumor assessments available and subject dose not die	Date of first administration of study treatment	Censored
4	No death or PD/relapse by the time of data cut-off for final analysis	Date of last adequate tumor assessment prior to or on analysis data cutoff date	Censored
5	Early discontinuation (lost to follow-up or withdrawal of consent) of study without death or PD/relapse	Date of last adequate tumor assessment	Censored
6	Subsequent anti-tumor therapy started prior to PD/relapse or death	Date of last adequate assessment prior to or on date of initiation of subsequent therapy visit	Censored
7	PD/relapse or death after missed or inadequate two or more consecutive tumor assessment visits	Date of last adequate tumor assessment prior to missed visits or date of first administration of study treatment (if no post-baseline tumor assessment)	Censored

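### A never-assessed patient who dies at any time, even after other therapy, is scored best response PD, against the SAP's own evaluation period and PFS rules

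*SAP*

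**What the plan says.** SAP 4.2.1 determines BOR from time point responses up to the earliest of several cut-offs. The last of these is "iii) receiving subsequent anti-cancer therapy, whichever is earlier". The section then adds a rule for patients with no post-dose assessment: if the investigator noted clinical progression, or they "have died due to any cause before their second post-dose tumor assessment, BOR will be PD".

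SAP 3.1.5 carries the same condition into the response evaluable set. Besides patients with an evaluable assessment, it admits those in the efficacy set with a baseline assessment who "ii) do not have post-dose tumor assessment, but have clinical progression as noted by the investigator or have died due to any cause", with the same reference to a second assessment.

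SAP 4.2.1 also lists reasons to be tabulated for patients whose BOR is NE. Two can apply to an unassessed patient: "All post-baseline overall responses are NE / No baseline or post-baseline assessments" and "Initiation of subsequent anti-tumor therapy prior to the first post-baseline tumor assessment".

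For PFS, SAP 4.2.7 Table 7 handles comparable patients as follows.
- Rule 2 counts as an event a "death on or before the second scheduled visit".
- Rule 6 censors when subsequent therapy comes before progression or death.
- Rule 7 censors a death that follows two or more missed assessments, at first dose if there was no post-baseline assessment.

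Protocol 6.1.19 keeps deaths coming in long after treatment: "All patients will be followed for survival status every 12 weeks", until death, loss to follow-up or withdrawal of consent.

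**The concern.** The rule's only time limit is an event that cannot happen to the patients it covers. Someone with no assessment never reaches a second one, so any recorded death satisfies the condition. Nor does the rule mention subsequent therapy, so a death months into another treatment is recorded as progression on HMPL-306.

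At stake is what the BOR table and the sensitivity analysis mean. The PD count would mix early failures with late deaths that say nothing about response to the drug. One patient could be PD for best response and censored at first dose for PFS. Two programmers could also treat an unassessed patient who took new therapy and later died differently, because the SAP does not say whether the imputation or the NE route comes first.

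**Working it through.** **Inputs.** Tumor assessments fall on Day 1 of Cycles 3, 5 and 7 (Protocol 6.1.14), with 28-day cycles. The second scheduled assessment is therefore Day 4 × 28 + 1 = 113, or Day 120 with the 7-day window. SAP 4.2.3(b) sets its early-period threshold for two missed assessments at 2 × (8 × 7 + 7) = 126 days, which reproduces. Its wording measures from a tumor assessment; I assume it runs from the first Cycle 1 dose when there is none.

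**Rules side by side.** None of these patients has a post-dose assessment or noted clinical progression; all have a baseline assessment.

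| Patient | BOR by the imputation rule | Response evaluable, 3.1.5(ii) | PFS, Table 7 |
|---|---|---|---|
| Dies at Week 6, no new therapy | PD | Yes | Event (Rule 2) |
| Dies at Month 8, no new therapy | PD | Yes | Censored at first dose (Rule 7) |
| New therapy at Week 5, dies at Month 10 | PD, although the evaluation period closed at Week 5 | Yes | Censored (Rule 6) |
| New therapy at Week 5, alive at cutoff | NE | No | Censored |

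The rules agree for the first and last patients. For the middle two, BOR and PFS diverge. The third and fourth had the same course up to the new therapy; only a later death separates PD from NE.

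**Effect on the primary analysis.** ORR and CBR count responses, or responses plus qualifying SD, over the efficacy analysis set (SAP 4.2.2, 5.2.9). PD and NE are both outside the numerator and inside the denominator, so the change is zero. The same holds for the CR and composite CR rates.

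**Effect on the sensitivity analysis.** Let n be treated patients, x responders, and u unassessed patients who die late or after new therapy, with everyone else evaluable. ORR is x/n as written and x/(n − u) with a bound. The values of x and u are assumed; n of 24 and 30 are the ends of the planned Part 1 range. Intervals are Clopper-Pearson 95%.

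| n, x | As written | u | With a bound |
|---|---|---|---|
| 30, 6 | 20.0% (7.7 to 38.6) | 1 | 6/29 = 20.7% (8.0 to 39.7) |
| 30, 6 | 20.0% | 3 | 6/27 = 22.2% (8.6 to 42.3) |
| 30, 6 | 20.0% | 6 | 6/24 = 25.0% (9.8 to 46.7) |
| 24, 5 | 20.8% (7.1 to 42.2) | 1 | 5/23 = 21.7% (7.5 to 43.7) |
| 24, 5 | 20.8% | 5 | 5/19 = 26.3% (9.1 to 51.2) |

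Efficacy is tabulated by dose level (SAP 5.1.1). With one responder and one such patient, a cohort of 3 goes from 1/3 = 33.3% to 1/2 = 50.0%, and a cohort of 6 from 1/6 = 16.7% to 1/5 = 20.0%.

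**How late deaths fall.** Under an assumed exponential curve, the share of 12-month deaths after Day 126 is [S(126) − S(365)] / [1 − S(365)]. At the 1.5-month median cited in Protocol 2.3.1 this is (0.148 − 0.004) / 0.996 = 14%. At assumed medians of 3, 6 and 9 months it is 34%, 49% and 55%. This describes the timing of all deaths, not the number of unassessed patients. The curve is rough: a 1.5-month median implies 0.5^8 = 0.4% alive at one year, against the 8% the protocol also cites.

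**The case against.** **The intended meaning is probably the second scheduled assessment.** Table 7 Rule 2 suggests so, and read that way the death rule has a limit. But neither 3.1.5 nor 4.2.1 says it, and that reading leaves subsequent therapy and the timing of clinical progression unaddressed. It could also be argued that the closing of the evaluation period already governs the imputation. That is possible, but the imputation is written as a separate provision that uses no time point responses, so a programmer need not read it so.

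**A reader might infer that the NE list flatly contradicts the rule.** It does not. It tabulates reasons for patients whose BOR is already NE and assigns no category. What is missing is the order of precedence.

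**A reader might infer that a patient with a non-evaluable first assessment who then dies meets neither limb of 3.1.5.** That rests on a strict reading. Limb (ii) can be taken as the complement of limb (i), meaning no evaluable assessment. The wording is worth tightening, but the gap is not established.

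**A reader might infer that reported response rates drift down as follow-up lengthens.** The main rates cannot, and for the sensitivity rate the point is largely hypothetical: one final analysis is planned with no formal interim (SAP 6.1, 6.2), and the study ends at most one year after the last patient's first visit (Protocol 6.1.20).

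**Such patients should be uncommon.** This stands. Bone marrow examination is due at the EOT visit (Protocol 6.1.10.3), tumor evaluation runs through EOT (6.1.14), and patients stopping for reasons other than progression continue assessments until progression or new therapy (6.1.14, 6.1.19). The rule reaches only those who miss all of these, and some will be PD anyway through early clinical progression.

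**The rule as written is conservative.** This also stands: it keeps deaths in the sensitivity denominator.

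**Conclusion.** The point holds as a misclassification rule with limited reach. As written, SAP 3.1.5(ii) and 4.2.1 turn any death of a never-assessed patient into PD and, given a baseline assessment, evaluable status. This is inconsistent with the BOR evaluation period and with Table 7 Rules 2, 6 and 7, and no precedence over the NE reasons is stated.

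The documents do not support a claim that the primary response results are wrong or biased: those do not change, and no hypothesis is tested. The effect is confined to the PD/NE split, the NE-reason counts and one sensitivity denominator. Its size depends on an unknown number of patients. It is probably small overall, within about 1 to 6 percentage points under the assumed counts and well inside the confidence intervals, and can be larger in dose cohorts of 3 to 6. It is worth correcting before database lock because the change is cheap and the SAP's PFS rules already show how.

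**What to change.** In SAP 3.1.5(ii) and 4.2.1, limit the rule to patients with no evaluable post-dose tumor assessment whose clinical progression or death occurs on or before the second scheduled post-dose assessment, with the same window as for PFS, and before any subsequent anti-cancer therapy. Classify all others without an evaluable assessment as NE. State that subsequent therapy before the first assessment takes precedence.

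Use one limit throughout. Table 7 Rule 2 gives no day number and SAP 4.2.3(b) already uses 126 days for two missed early assessments; a separate Day 120 cutoff for BOR would add a third convention. State that limit once, measured from the first Cycle 1 dose when there is no assessment, and refer to it from 3.1.5, 4.2.1 and Table 7.

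The cost is a sentence in two sections, a cross-reference and a date check in programming. The downside is that a few late deaths leave the sensitivity denominator, so that ORR becomes slightly higher and less conservative. The primary analysis still counts those patients as non-responders.

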4.2.2. Composite Response, Objective Response Rate and Clinical Benefit Rate

Some composite response categories are defined as following based on BOR.

- Composite complete response (cCR)-1: including the response category of CR_{MRD-} , CR, CRh, and CRI;
- cCR-2: including the response category of CR_{MRD-} , CR and CRh;
- cCR-3: including the response category of CR_{MRD-} and CR;

CR rate by 24 weeks is defined as the proportion of patients with BOR being CR by 24 weeks during the tumor evaluation period. The protocol allows a 1-week window for disease assessments. Therefore, a patient will be considered to have achieved “CR by 24 weeks” if the date of first CR is within 25 weeks (24 weeks target+1 week window) after the date of first study drug administration: CR by 24 weeks if date of first CR minus (–) date of first study drug administration $+1 \leq 24 \times 7 + 7$. The cCR-1 rate by 24 weeks, cCR-2 rate by 24 weeks, and cCR-3 rate by 24 weeks will be similarly calculated.

Objective response rate (ORR) is defined as the proportion of patients with BOR being CR_{MRD}-, CR, CRh, CRi, MLFS, or PR.

Clinical benefit rate (CBR) is defined as the proportion of patients with BOR being CR_{MRD}-, CR, CRh, CRi, MLFS, PR, or SD lasting for 3 cycles.

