6.1.14 Efficacy Evaluation

Efficacy evaluation of AML will be performed based on 2017 European LeukemiaNet (ELN) criteria ([Appendix 8](#)). Efficacy evaluation of HR-MDS will be performed based on the International Working Group response criteria in myelodysplasia ([Appendix 12](#)). Efficacy evaluation of AITL will be performed based on Lugano Classification ([Cheson 2014](#)) for Hodgkin and Non-Hodgkin's Lymphoma ([Appendix 9](#)).

Tumor evaluations will be conducted at screening, every 8 weeks (± 7 days) during the first 24 weeks (ie, Day 1 of Cycles 3, 5, and 7), and every 12 weeks (± 14 days) thereafter (ie, Day 1 of Cycles 10, 13, and so on) through EOT, or end of Efficacy Follow-up period (if applicable). Patients who discontinue HMPL-306 treatment due to reasons other than disease progression will continue tumor assessment according to previous tumor evaluation schedule until disease progression, as defined in [Appendix 8](#) and [Appendix 9](#), or start of new antineoplastic therapy (see [Table 1](#)). The same imaging procedure and laboratory tests used to define measurable lesions at baseline should be used throughout the study for each patient.

The baseline tumor assessment should be completed within 28 days prior to the first dose of study treatment (depending on the patient's disease status, a window may be acceptable based on a discussion between the investigator and the sponsor's medical monitor). Tumor assessments completed as standard of care, prior to signing of the informed consent and within 28 days of first dose of study treatment, may be used as baseline assessment.

Response evaluation of patients will be based on the most recent results of physical, bone marrow (if applicable), imaging, and hematological examinations, per local assessment. If a patient needs to delay the study drug after bone marrow examination and wait for recovery of peripheral blood count, then routine blood test results within 2 weeks after bone marrow analysis can be used to determine response.

For patients with myeloid malignancies, this assessment should be done using a blood test, bone marrow aspiration and/or biopsy, and physical examination as per the Schedule of Events (see [Table 1](#)).

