2.2 Study Design

This is a phase 1, open-label, multicenter, single-arm study to evaluate safety, tolerability, PK, PD and preliminary efficacy of HMPL-306 administered orally in treatment of patients with advanced relapsed, refractory, or resistant hematological malignancies that harbor IDH mutations. The study consists of 2 parts: dose escalation part (Part 1) and dose expansion part (Part 2).

The first part of the study is dose escalation, where cohorts of patients will receive ascending oral doses of HMPL-306 to determine MTD and/or the RP2D. The modified toxicity probability interval-2 (mTPI-2) ([Greenberg 2012](#), [Guo 2017](#)) design will be used to perform dose escalation and MTD/RP2D determination. Briefly, the mTPI-2 method uses a Bayesian framework and a hierarchical model to compute the dose escalation based on the interval between the toxicity rate of each dose level and target probability ([Greenberg 2012](#), [Guo 2017](#)). This study is designed targeting a DLT rate of 20% with an equivalence interval of 15% to 25%.

Seven days prior to initiating daily administration of HMPL-306 from Cycle 1 Day 1 (C1D1), patients enrolled in each cohort during dose escalation will be administered a single oral dose of HMPL-306 on Day -7 relative to C1D1 (Day 1 of PK week). Serial blood samples will be collected from Days 1 to 7 of the PK week for analysis of plasma concentrations of HMPL-306 and 2-HG.

A cycle of study treatment is defined as 28 days of continuous daily dosing. After the PK week, dose escalation will start at **[REDACTED]** mg QD orally (PO) for Cohort 1 and then escalate in the sequence of **[REDACTED]** mg QD, and **[REDACTED]** mg QD.

Safety monitoring and evaluation of dose escalation will be carried out by the Safety Review Committee (SRC), which is comprised of the sponsor and investigators.

[figure not shown]
In the dose-expansion part, 1 cohort of patients will receive HMPL-306 at MTD and/or RP2D to evaluate further the safety, tolerability, PK, PD, and preliminary efficacy in approximately 10 patients with advanced relapsed, refractory, or resistant hematological malignancies with IDH mutations. Patients enrolled in the dose expansion part must not have standard therapeutic options available (including IDH inhibitors where approved) and must have the following:

- Relapsed AML unsuitable for intensive chemotherapy or venetoclax-based regimen or target agents;

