4. ENDPOINTS

4.1. General Principles for Derived and Transformed Data

4.1.1. Reference Start Date and End Date and Study Day

(1) Reference start date

Dose escalation part:

For efficacy analysis, reference start date (Day 1) is defined as the first date when a non-zero dose of study treatment in continuous dosing cycle (i.e. excluding single oral dose from the PK week) is administrated.

For safety analysis, reference start date (Day 1) is defined as the first date when a non-zero dose of study treatment (i.e. including single oral dose from the PK week) is administrated.

Dose expansion part:

Reference start date (Day 1) is defined as the first date when a non-zero dose of study treatment is administrated.

(2) Reference end date

Reference end date is defined as the last date when a non-zero dose of study treatment is administered.

(3) Study day

Study day will be calculated from the reference start date, and it will be used to show start/stop day of assessments or events relative to the start date of study treatment.

- If the date of the event is on or after the reference start date, study day = (date of event – reference start date) + 1.
- If the date of the event is prior to the reference start date, study day = (date of event – reference start date).

Note that, the day of the first dose of study drug is day 1 and the day before it is day – 1, not day 0.

In the situation where the event date is partial or missing, the date will appear partial or missing in the listings.

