4.2.5. Event-free Survival

Event-free survival (EFS) is defined as the time from date of first study drug administration from Cycle 1 in continuous cycle (i.e. not from the date of single oral dose from the PK week for the dose escalation part) to treatment failure, relapse from CR (including CR_{MRD}-, CR, CRh and CRi), or death due to any cause, whichever occurs first. EFS analysis will take competitor Ivosidenib Phase III EFS definition and censoring rules as reference ([Xu et al, 2020](#)). Treatment failure is defined as failure to achieve CR (including CR_{MRD}-, CR, CRh and CRi) by Week 24. Subjects who do not achieve CR (including CR_{MRD}-, CR, CRh and CRi) by Week 24 will be considered to have had an event at Day 1 of first study drug administration from Cycle 1 (i.e. not from the date of single oral dose from the PK week for the dose escalation part). For the remaining CR responders (including CR_{MRD}-, CR, CRh and CRi), the event time will be the time of either disease relapse or death due to any cause, whichever occurs first. A response of CR (including CR_{MRD}-, CR, CRh and CRi) represents both disease control and establishment of hematopoiesis in subjects with AML and is an important predictor of OS ([Dombret et al, 2015](#)). Event-free survival will be censored upon initiation of a subsequent anticancer therapy.

The outcome (event or censor), type of event and the date of event or censoring to be considered for the EFS are presented in [Table 4](#).

Table 4 Outcome and Event or Censoring Dates for EFS

Rule	Situation	Date of Event or Censoring	Outcome
1	CR by 24 weeks ^a then relapse between scheduled visit or after one missing tumor assessment visit	Date of relapse	Event (relapse)
2	CR by 24 weeks ^a then death (no relapse) between scheduled visit or after one missing tumor assessment visit	Date of death	Event (death)
3	On treatment \geq 24 weeks without CR by 24 weeks ^a	Date of first administration of study treatment	Event (TF, on treatment \geq 24 weeks without CR)
4	Treatment discontinuation prior to 24 weeks, without CR by 24 weeks ^a	Date of first administration of study treatment	Event (TF, treatment discontinuation prior to 24 weeks without CR)
5	On treatment $<$ 24 weeks without CR and active in study	Date of the last adequate disease assessment	Censored

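### SAP 4.2.2: the formula for CR by 24 weeks stops at Day 175, one day before the 24-week assessment window closes on Day 176

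*SAP*

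**What the plan says.** SAP 4.2.2 defines the CR rate by 24 weeks and gives the reason for its extra week: "The protocol allows a 1-week window for disease assessments". In words, the rule is that the "date of first CR is within 25 weeks (24 weeks target+1 week window) after the date of first study drug administration". It then restates the rule as a formula: date of first CR minus "date of first study drug administration $+1 \leq 24 \times 7 + 7". The composite rates by 24 weeks (cCR-1, cCR-2, cCR-3) are to be calculated in the same way.

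Protocol 6.1.14 schedules tumor evaluations every 8 weeks, ±7 days, in the first 24 weeks, and ties them to named visits: "ie, Day 1 of Cycles 3, 5, and 7". On cycle length, SAP 2.2 states: "A cycle of study treatment is defined as 28 days of continuous daily dosing". On day numbering, SAP 4.1.1 states that "the day of the first dose of study drug is day 1", with no Day 0.

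SAP 4.2.5 treats failure to reach CRMRD-, CR, CRh or CRi by Week 24 as EFS treatment failure. Such a patient "will be considered to have had an event at Day 1 of first study drug administration from Cycle 1". Table 4 footnote a allows a one-week window based on the protocol's assessment schedule, but does not restate the formula.

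**The concern.** The extra week exists so that a 24-week assessment done within its permitted window still counts. The formula uses a day count in which the first dose is Day 1, but adds the 7 days to 168 rather than to Day 169, the scheduled visit. The last permitted day is therefore excluded. The same passage also gives two different cut-offs, one in words and one in symbols, so two programmers could code different rules and both could claim to follow the SAP.

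The cut-off decides whether a patient is a 24-week responder. Efficacy is summarized by dose level in Part 1 (SAP 5.1.1), and a dose level has at least 3 patients, extendable to 12 (Protocol 4.1.1). One reclassified patient moves a rate by 1/3 (33 percentage points) at n = 3, or by 1/12 (8 points) at n = 12. For EFS the error could be larger for that patient, whose responder time would be replaced by an event at Day 1.

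**Working it through.** **Inputs**
- Cycle length: 28 days (SAP 2.2).
- First dose is Day 1, no Day 0 (SAP 4.1.1).
- 24-week evaluation: C7D1, ±7 days (Protocol 6.1.14).
- Formula: date of first CR − date of first dose + 1 ≤ 24 × 7 + 7 (SAP 4.2.2).

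**1. The SAP's own figure.** 24 × 7 + 7 = 175. The left side of the formula is the study day, so the cut-off is Day 175.

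**2. The visit and its window.** C7D1 = 6 × 28 + 1 = Day 169. The window runs from 169 − 7 = Day 162 to 169 + 7 = Day 176, which is 15 days.

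**3. Check against the SAP's other thresholds.** The missed-assessment rules in SAP 4.2.3 use (16 − 1) × 7 + 1 = 106 and (24 − 1) × 7 + 1 = 162. C5D1 is 4 × 28 + 1 = Day 113, and 113 − 7 = 106. For C7D1, 169 − 7 = 162. Both agree with the lower window edges, so the SAP elsewhere is consistent with C7D1 on Day 169. The matching upper edge is Day 176.

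**4. A first CR on Day 176.** The date difference is 175, and 175 + 1 = 176 > 175, so the formula rejects it. Days 162 to 175 pass. That is 14 of 15 days accepted and 1 rejected.

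**5. The words instead of the formula.** Within 25 weeks after the first dose, taken literally, is a date difference of at most 25 × 7 = 175, which is Day 176. On that reading all 15 days pass. The words and the formula differ by one day.

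**6. No later visit repairs it.** The next scheduled evaluation is C10D1 (Protocol 6.1.14): 9 × 28 + 1 = Day 253, or Day 239 at the earliest with the 14-day window.

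**7. EFS, if the same formula is used.** Suppose Day 176 is the first CRMRD-, CR, CRh or CRi in a patient on treatment for at least 24 weeks. Table 4 rule 3 then gives an event at first administration (rule 4 if treatment stopped earlier). Rules 1, 2, 6, 7 and 8 all require CR by 24 weeks, so none of them restores the patient as a responder.

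**8. With the corrected constant.** 24 × 7 + 1 + 7 = 176, and all 15 window days qualify.

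**The case against.** The best defense is that 24 weeks plus one week is 168 + 7 = 175, which is what the formula gives, and that SAP 4.2.2 never mentions C7D1. If the 24-week visit were Day 168, its window would end on Day 175 and there would be no gap. That does not stand, because the protocol fixes the visit at Day 1 of Cycle 7 and the SAP's own Day 162 threshold agrees with it. The ±3-day window for ordinary Cycle 3 and later visits would end on Day 172, but tumor evaluation has its own ±7 days.

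Other limits do stand, and they rule out stronger readings that a reader might infer:

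- **That EFS is certainly affected.** Table 4 footnote a refers to the protocol schedule and a one-week window. Applied directly to C7D1, it covers Day 176. The Day 1 event follows only if the 4.2.2 formula is reused for Table 4.
- **That the patient is lost from every 24-week rate.** This needs a first CR-type response of CR on exactly Day 176. An earlier CRi keeps the patient in cCR-1, an earlier CRh in cCR-1 and cCR-2, and either one prevents EFS treatment failure.
- **That the Part 1 clock starts at the PK-week dose.** SAP 4.2.2 omits the Cycle 1 qualifier, and counting from a dose 7 days earlier would put even an on-schedule C7D1 at Day 176, past the cut-off. The SAP excludes that reading. Section 4.1.1 starts the efficacy clock at continuous dosing, 4.2.1 counts best overall response from Cycle 1, and 4.2.5 does the same for EFS.
- **That 1 day in 15 means about 7% of patients.** It is a share of calendar days. Most first responses may come at C3D1, C5D1 or well inside the C7D1 window, and the documents give no distribution of visit dates.

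**Conclusion.** The formula in SAP 4.2.2 is one day short of the window it is meant to cover, and it disagrees by one day with its own wording. This rests on C7D1 being the 24-week assessment, 28-day cycles, and first dose as Day 1, all of which the documents state.

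The size is 1 of 15 window days. A first response on Day 176 is left out of the 24-week rates it would otherwise enter. The EFS consequence is conditional on reuse of the formula and on Day 176 being the first CRMRD-, CR, CRh or CRi. The study plans no hypothesis test (SAP 5.2.9) and EFS is a secondary endpoint, so this is a small correction that need not change any conclusion. It is still worth making, because it is a classification rule that is wrong as written.

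**What to change.** In SAP 4.2.2, write the criterion as date of first CR − C1D1 date + 1 ≤ 24 × 7 + 1 + 7 = 176, for the CR rate and the three composite rates by 24 weeks. In Table 4 footnote a, refer to that criterion so that EFS and the response rates use one rule. Naming C1D1 only makes 4.2.2 consistent with 4.1.1 and does not change the intended start date.

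The cost is one constant, one phrase and one cross-reference. If the database is already locked, check whether any first response falls on Day 176 and record the result in the clinical study report, where SAP section 1 says deviations are to be documented.
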